#### 4.2.1. Diary

Baseline for diary-based efficacy variables (total reliever bronchodilator medication, █) will be defined as the average of the values over the 7 days preceding the first dose of reslizumab in this study. At least 4 out of the 7 expected measurements need to be recorded for each diary variable; otherwise the baseline value for that variable will be treated as missing. This definition will exclude daily morning ambulatory FEV1 whose baseline value will be derived as outlined in Section 4.2.2.

For non-seamless rollovers, baseline will be derived from data collected in this study during 7-day run-in period prior to Visit 1. For seamless rollovers, baseline will be derived from data collected during the 7 days preceding the EOT visit of the previous study (30025 or 30027).

#### 4.2.2. Spirometry

Pre-bronchodilator FEV1 at pre-specified clinic visits and daily morning ambulatory FEV1 will be measured using a handheld device that has combined spirometry and eDiary capabilities.

The baseline value for pre-bronchodilator FEV1 measured at the clinic visits will be the last observed value prior to the first dose of reslizumab in this study. The baseline value for daily morning ambulatory FEV1 will be defined similarly.

For non-seamless rollovers, baseline will be derived from data collected in this study on or prior to Visit 1. For seamless rollovers, baseline will be derived from data collected at the EOT visit of the previous study (30025 or 30027).

#### 4.2.3. Patient Reported Outcomes

The baseline value for patient reported variables (ACQ-6, AQLQ +12) will be the last observed value prior to the first dose of reslizumab in this study.

For non-seamless rollovers, baseline will be derived from data collected in this study on or prior to Visit 1. For seamless rollovers, baseline will be derived from data collected on the same day as the EOT visit of the previous study (30025 or 30027).

**4.2.4. Oral Corticosteroid Dose**

The baseline value will be defined as the OCS dose reported on the day of first dose of reslizumab in this study.

**4.2.5. Biomarkers**

The baseline value for blood eosinophil levels will be the last observed value prior to the first dose of reslizumab in this study.

For non-seamless rollovers, baseline will be derived from data collected in this study on or prior to Visit 1. For seamless rollovers, baseline will be derived from data collected on the same day as the EOT visit of the previous study (30025 or 30027).

**4.2.6. Safety**

The baseline value for all visit-based safety assessments (eg, laboratory, vital signs, physical examination, ECG) will be the last observed value prior to the first dose of reslizumab in this study.

For non-seamless rollovers, baseline will be derived from data collected in this study on or prior to Visit 1. For seamless rollovers, baseline will be derived from data collected on the same day as the EOT visit of the previous study (30025 or 30027).

**4.2.7. ADA**

The baseline value for all ADA status will be the last observed value prior to the first dose of reslizumab in the previous double-blind study (30025 or 30027).

For both seamless and non-seamless rollovers, baseline will be derived from data collected on the same day as the day of randomization (DOR) visit of the previous study (30025 or 30027).

**4.3. Handling Withdrawals and Missing Data**

In general, missing data will not be imputed, unless otherwise specified.

**4.4. Study Days and Visits**

Study days will be numbered relative to the first day of study drug administration. The start of treatment (day 1) is defined as the date on which a patient takes the first dose of study drug in this study. Days will be numbered relative to study start (ie, ..., -2, -1, 1, 2, ...) with day 1 being the start of study drug and day -1 being the day before the start of study drug).

For safety-by-visit summaries, if there are multiple assessments at a post-baseline visit then the last non-missing assessment at that visit will be used for the summary. This includes assessments at the scheduled and unscheduled visits.

For efficacy by-visit summaries, only the assessments at the scheduled visit will be summarized. The assessments at unscheduled visits will only be listed. For the purpose of the efficacy analysis, assessments collected at an early termination visit will be considered as the next scheduled visit for that assessment if at least 3, but no more than 5 weeks, elapsed since the date of the last dose of study drug.

“Endpoint” for safety and efficacy analyses summaries is the time point when the last observation was obtained during the treatment period. For patients who completed treatment in this study, the treatment period will be defined from the first dose of study drug to the end of treatment (week 36) visit. For patients who prematurely discontinue treatment, the treatment period will be defined from the first dose of study drug to the last dose of study drug + 4 weeks.

For summaries of diary data and handheld spirometry data, the day used for analysis will consist of the evening assessment for the day and the morning assessment for the following day, as illustrated in [Table 1](#). Weekly average data will be generated using 7-day window intervals derived based on these analysis days.

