7.1.6.1.2. Creatine Phosphokinase/Muscular Adverse Events Case Report Form

Potentially clinically significant CPK elevations (with or without associated symptoms) or myalgia/muscle symptoms will be recorded as an adverse event and documented using the potentially clinically significant CPK/myalgia CRF. A potentially clinically significant CPK is defined as $\geq 3.1 \times$ ULN (grade 3 based on the FDA “Guidance for Industry Toxicity Grading Scale for Healthy Adult and Adolescent Volunteers Enrolled in Preventative Vaccine Clinical Trials”).

If a potentially clinically significant CPK level ($\geq 3.1 \times$ ULN) occurs, the patient should attend an unscheduled visit for a physical examination as well as additional testing, if indicated per investigator judgement. CPK levels will be retested at a minimum of every 7 to 10 days until the elevation is resolved or if agreed with the medical monitor that no further testing is indicated. For $\geq 10 \times$ ULN elevations in CPK, repeat CPK level, urinalysis (including microscopy), serum electrolytes, blood urea nitrogen (BUN), and creatinine will be performed as soon as possible after receipt of the CPK result. Further testing of CPK levels should be undertaken as frequently as needed to manage patient care per investigator judgment but should be at a minimum of every 7 to 10 days as above. Need for repeat urinalysis, serum electrolytes, BUN, and creatinine testing should be determined by the investigator. In addition, need for treatment (eg, administration of iv fluids and urine alkalinization) should be considered by the investigator.

In cases deemed by the investigator to be treatment-related elevations in CPK $\geq 10 \times$ ULN (eg, potentially rhabdomyolysis), study drug discontinuation should occur at least until CPK normalization or longer based on investigator clinical assessment in collaboration with the sponsor.

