7.7. Vital Signs

Vital signs (blood pressure [systolic/diastolic], respiratory rate, body temperature, and pulse) will be measured at the time points detailed in [Table 1](#). All vital signs results outside of the reference ranges will be judged by the investigator as belonging to one of the following categories:

- abnormal and not clinically significant
- abnormal and clinically significant

Before blood pressure and pulse are measured, the patient must rest in a supine or semi-erect/seated position for at least 5 minutes (the same position and arm should be used each time vital signs are measured for a given patient). For any abnormal vital sign value, the measurement should be repeated as soon as possible. Any vital sign value that is judged by the investigator as clinically significant will be recorded both on the source documentation and the CRF as an adverse event and will be monitored as described in [Section 7.1.2](#).

In addition, potentially clinically significant values will be predefined by the sponsor for selected vital sign parameters and will be detailed in the statistical analysis plan.

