#### 8.5. Clinical Laboratory Tests

Clinical laboratory tests (serum chemistry and hematology) will be performed prior to reslizumab administration at the time points detailed in Table 1 of the protocol. Clinical

laboratory tests will be performed using the central laboratory. Specific laboratory tests to be performed are provided in protocol section 7.4.1.

Summary statistics for laboratory tests will be presented at each scheduled visit. Actual values and changes from baseline to each visit will be summarized using descriptive statistics. Shifts (below, within, and above the normal range) from baseline to each visit will be summarized using patient counts and percentages. Shifts from baseline (Grade 0-4) will be provided for creatine phosphokinase (CPK) at each visit, based on the following grading scale:

- **Grade 0:** <1.25 x ULN
- **Grade 1:** 1.25 to 1.5 x ULN
- **Grade 2:** 1.6 to 3 x ULN
- **Grade 3:** 3.1 to 10 x ULN
- **Grade 4:** >10 x ULN

For CPK values  $\geq 3.1 \times \text{ULN}$  (Grade 3-4), investigators will collect additional information promptly from the patient related to symptoms associated with the elevation and any potential alternate causes. This supplemental data will be reported in the patient listings.

The incidence of potentially clinically significant abnormal values will be summarized for laboratory data using descriptive statistics with the criteria specified in [Table 5](#); criteria have been provided for adults and adolescents separately.

Summaries of potentially clinically significant laboratory values will include all relevant post-baseline values (including scheduled, unscheduled, and early termination visits). A post-baseline laboratory value will be considered potentially clinically significant only if it satisfies the specified criteria and is more extreme (farther from the limit) than the baseline value. Listings for potentially clinically significant laboratory data will be presented. If any patient has a positive pregnancy test, relevant information will be supplied in data listings.

A scatter plot will be provided for the baseline and maximum value for CPK.

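### The SAP's last-value rule for by-visit safety tables includes unscheduled values but has no visit-assignment rule, so a resolved CPK retest can stand in for the Grade 3-4 value that triggered it

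*SAP*

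**What the plan says.** **Selection rule.** SAP 4.4 states for safety by-visit summaries that "if there are multiple assessments at a post-baseline visit then the last non-missing assessment at that visit will be used for the summary", and adds: "This includes assessments at the scheduled and unscheduled visits". The next paragraph takes the opposite line for efficacy: "For efficacy by-visit summaries, only the assessments at the scheduled visit will be summarized", with unscheduled efficacy values only listed.

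**CPK displays.** SAP 8.5 says "Summary statistics for laboratory tests will be presented at each scheduled visit". It also says "Shifts from baseline (Grade 0-4) will be provided for creatine phosphokinase (CPK) at each visit". No shift to the worst post-baseline grade is planned.

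**Retesting.** Protocol 7.1.6.1.2 calls for an unscheduled visit when CPK is at least 3.1 x ULN. It then says "CPK levels will be retested at a minimum of every 7 to 10 days until the elevation is resolved", or until the medical monitor agrees that testing can end. At 10 x ULN or more, the repeat is to be done as soon as possible after the result arrives.

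**Vital signs.** Protocol 7.7 says: "For any abnormal vital sign value, the measurement should be repeated as soon as possible". SAP 8.7 summarizes vital sign values and changes by visit.

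**Grade scale.** SAP 8.5 defines Grade 1 as 1.25 to 1.5, Grade 2 as 1.6 to 3, Grade 3 as 3.1 to 10, and Grade 4 as above 10, all x ULN.

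**The concern.** Protocol-mandated CPK retests exist only for patients whose value was already at Grade 3 or above, and they normally end when the value has come down. If the last value at a visit is kept, and the retest counts as being at that visit, the table drops the value that triggered the follow-up and shows the one that closed it. A patient with a normal scheduled value has no mandated retest, so no matching correction runs the other way.

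Musculoskeletal and CPK abnormalities are a named safety interest in Protocol 2.1.1, and SAP 8.3.1.5 gives muscle disorders their own summary. At stake is whether the by-visit means, changes and Grade 0-4 shifts describe CPK at the scheduled visit or CPK after follow-up. A reader could meet a patient counted as Grade 3-4 in the PCS table who appears as Grade 0 to Grade 0 in the shift table, with nothing in the plan to explain the difference.

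Abnormal vital signs raise a similar but smaller issue. The prompt repeat is taken only when the first reading is abnormal, and it becomes the last reading at that visit.

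**Working it through.** The plan gives no figure to reproduce here. The check traces the rules and then asks how often a retest falls at the same visit as its trigger.

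**Step 1. How an unscheduled value can enter.** SAP 8.5 shows laboratory statistics at scheduled visits only. SAP 4.4 lets unscheduled values into the safety by-visit selection. Such a value can therefore reach these tables only by being attached to a scheduled visit. The SAP has no laboratory visit window and no exception for CPK, so the attachment is left to the programmer.

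**Step 2. Timing inputs.** Post-baseline chemistry is scheduled at weeks 4, 8, 24 and 36, each ±7 days (Protocol Table 1). Retest gaps are 7 to 10 days (Protocol 7.1.6.1.2). Let u be the draw day relative to nominal (-7 to +7, 15 values) and g the gap (7, 8, 9 or 10 days). That gives 15 × 4 = 60 combinations, weighted equally by assumption. The k-th retest falls on day u + k·g relative to the nominal visit.

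**Step 3. Share of retests at the same visit, under three assumed assignment rules.**

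| Assumed rule | Visit | First retest | Second retest |
|---|---|---|---|
| Until the next visit's window opens | Week 4 | 60/60 = 100% | 44/60 = 73% |
| | Weeks 8, 24 | 100% | 100% |
| Midpoint to the next chemistry visit | Week 4 (midpoint +14 days) | 54/60 = 90% | 20/60 = 33% |
| | Weeks 8, 24 (midpoints +56, +42 days) | 100% | 100% |
| ±7 days only | Any | 26/60 = 43% | 1/60 = 2% |

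For the last row, the first retest counts if u + g ≤ 7. That gives 8 + 7 + 6 + 5 = 26 combinations for g = 7, 8, 9 and 10. If the draw is on the nominal day, only g = 7 qualifies, or 1/4 = 25%. Week 36 under the first two rules depends on whether retests after the end-of-treatment visit are counted. SAP 4.4 ends the treatment period at that visit for completers.

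The 7 to 10 day interval is a minimum frequency. Values of 10 x ULN or more are repeated sooner, so the most extreme values are the most exposed under narrow windows.

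**Step 4. Effect on one patient (assumed values).** Baseline is Grade 0, the scheduled week 8 value is 6.0 x ULN, and the retests are 2.5 and then 1.0 x ULN. If both retests are assigned to week 8:

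- scheduled value: 6.0, a shift of Grade 0 to Grade 3
- last value: 1.0, a shift of Grade 0 to Grade 0
- worst value: 6.0, a shift of Grade 0 to Grade 3

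If only the first retest is assigned to week 8, the last value is 2.5 and the shift is Grade 0 to Grade 2.

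**Step 5. Grade scale.** Values above 1.5 and below 1.6 x ULN have no grade; 1.55 is an example. Nor do values above 3 and below 3.1, such as 3.05. A value of exactly 10 x ULN is Grade 3 in the SAP but falls in the protocol's follow-up category of 10 x ULN and above.

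**The case against.** The strongest reply is that SAP 4.4 speaks of several assessments at one visit, and an unscheduled visit is a separate visit with its own date and reason. On that reading the rule works within each visit, a retest a week later never meets the scheduled value, and SAP 8.5 simply does not display it. This stands to the extent that replacement is not certain, and a reader who infers that the shift table must replace every Grade 3-4 value goes further than the documents do. It does not remove the problem. The efficacy rule in the same section expressly keeps unscheduled values out of by-visit summaries, while the safety rule expressly brings them in.

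A reader might also infer that Grade 3-4 CPK disappears from the report. It does not:

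- Every value of at least 3.1 x ULN is recorded as an adverse event, with or without symptoms (Protocol 7.1.6.1.2), and so contributes to the primary endpoint.
- The muscle-disorder summary includes the preferred term for increased blood CPK (SAP 8.3.1.5).
- PCS incidence uses all post-baseline values, with CPK Grades 3 and 4 as criteria (SAP 8.5 and Table 5).
- A baseline-versus-maximum CPK plot and listings are planned.

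Nor can a patient count be given. The documents report transient CPK elevations in 20% of iv reslizumab patients and 18% on placebo (Protocol 1.2.2.2.4), but no rate at 3.1 x ULN or above. Retesting may stop before resolution, and a last retest may still be Grade 3-4.

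Three smaller points are fair. An unscheduled visit made for another reason could put a high value in place of a normal one, so the bias is a tendency of the mandated retests and not a strict rule. By-visit and any-time displays normally differ, and a difference alone is no error. A prompt repeat of a vital sign is milder than weeks of CPK retesting, and PCS vital signs use all post-baseline values.

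**Conclusion.** The point holds for the by-visit displays. As written, SAP 4.4 together with result-triggered retesting can put a resolved CPK value in the place of the Grade 3-4 value that caused the retest, and the tendency is toward showing no elevation. By-visit vital sign tables can be affected in a similar way.

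The size depends on an assignment rule the SAP does not give. The first retest shares the trigger's visit in about 43% of timing combinations under ±7-day windows, and in 90-100% at weeks 4, 8 and 24 under the two wider rules. These shares assume uniformly spread draw days and 7 to 10 day gaps. They are shares of retests assigned to the visit, not of patients misgraded. That number cannot be derived from the documents.

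The primary endpoint and the incidence of Grade 3-4 CPK are not affected. The gaps in the grade scale are a separate, small defect that is certain from the text. The difference at exactly 10 x ULN is minor, since one boundary is a reporting grade and the other a follow-up category, but the two passages should be reconciled.

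**What to change.** - **SAP 4.4:** for by-visit safety summaries, use the scheduled-visit value, and an unscheduled value only if the scheduled one is missing. State how unscheduled values are assigned to visits, including those after the end-of-treatment visit. This brings safety close to the rule the SAP already uses for efficacy.
- **SAP 8.5:** add a CPK shift from baseline to worst post-baseline grade over all scheduled, unscheduled and early-withdrawal values. It overlaps with the PCS table and the maximum-CPK plot, but gives the grade shift that neither shows.
- **CPK grades:** make the reporting bands contiguous so that every value has a grade, and reconcile the SAP's Grade 4 boundary with the protocol's category at 10 x ULN.

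The cost is a few lines of SAP text and one extra table, with no new data. The by-visit CPK display may look slightly less favourable.

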 - Pre-bronchodilator spirometry assessments should only be performed after withholding short-acting bronchodilators (ie, inhaled short-acting beta-adrenergic agonists and/or short-acting anticholinergics) for at least 6 hours and long-acting bronchodilators (ie, inhaled long-acting beta-adrenergic agonists and long acting anticholinergic agents) for at least 12 or 24 hours, according to their labeled dose schedule.
- Complete asthma-specific tests (ACQ-6 and AQLQ12+) (week 8 and 24 only).
- Assess asthma exacerbations and related HCU.
- Reinforce eDiary, PEF/spirometry compliance, and rescue medication use.
- Perform adverse event inquiry.
- Perform concomitant medication inquiry (includes assessment of OCS dose if participants are on maintenance corticosteroids).
- Perform IMP administration.
- Observation at the study center for 1 hour after IMP administration
- Vital sign assessment for any reported symptoms during 1-hour observation.
- Assessment of injection site by study personnel approximately 1 hour after IMP administration.

Additionally, patients will complete a question regarding new symptoms on the handheld eDiary/spirometry device the evening after the IMP administration and the following morning as well as obtain PEF and FEV₁ measurements, and record rescue inhaler use.

4. Procedures at End of Treatment or Early Withdrawal (V_{EOT}, Week 36)

An EOT visit (week 36 \pm 7 days, [V_{EOT}]) will occur 4 weeks after the final administration of study drug or at the time of early withdrawal of the patient. The following procedures/assessments will be performed at this visit:

- Perform urine pregnancy testing (for female patients who are not postmenopausal or surgically sterile only).

- Perform hematology tests.
- Perform serum chemistry tests with CPK.
- Collect blood sample for immunogenicity (ADA) assessment.
- Perform full physical examination (should include the following organ systems: general appearance, HEENT, chest, lung, and heart, abdomen, musculoskeletal, skin, lymph nodes, and neurological).
- Perform ECG.
- Perform vital signs measurements.
- Measure height and weight.
- Perform pre-bronchodilator spirometry (FEV₁) using the handheld spirometry device.

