## 1. STUDY OBJECTIVES AND ENDPOINTS

### 1.1. Primary and Secondary Study Objectives and Endpoints

The primary objective of this study is to support the long-term safety of reslizumab 110 mg administered subcutaneous (sc) once every 4 weeks in patients 12 years of age and older with severe eosinophilic asthma that is inadequately controlled on standard-of-care treatment.

The primary endpoint is frequency of all adverse events including serious adverse events.

The secondary safety endpoints for this study include the following:

- clinical laboratory test results – hematology and chemistry results at baseline and at weeks 4 (chemistry only), 8, 24, and 36 or early withdrawal visit
- local tolerability at the injection site at approximately 1 hour after study drug administration every 4 weeks throughout the study
- vital signs measurements every 4 weeks throughout the study
- concomitant medication usage every 4 weeks throughout the study

The secondary objective of this study is to evaluate the efficacy of reslizumab 110 mg administered sc once every 4 weeks in patients 12 years of age and older with severe eosinophilic asthma that is inadequately controlled on standard-of-care treatment.

The secondary efficacy endpoints for this study include the following:

- clinical asthma exacerbation (CAE) and healthcare utilization (HCU)-related endpoints
  - frequency of CAEs
  - frequency of asthma-specific hospital admissions
  - length of hospital stay and number of Intensive Care Unit (ICU) days
  - frequency of asthma-specific emergency department visits
  - frequency of school/work days missed due to asthma
- change from baseline in pre-bronchodilator Forced Expiratory Volume in 1 Second (FEV1) measured using spirometry at weeks 0, 8, 24, and 36 or early withdrawal visit
- change in daily morning ambulatory FEV1 from baseline at each week through week 36 or early withdrawal, as measured by the handheld spirometry device.
- absolute and percent reduction in the daily Oral Corticosteroid (OCS) dose at weeks 20 and 36 or early withdrawal visit as compared with the dose at baseline (for patients on daily OCS at baseline).
- change from baseline in total inhalations of reliever bronchodilator medication (eg, short-acting beta agonist) measured using weekly averages until week 36 or early withdrawal visit.

- change from baseline in Asthma Control Questionnaire (ACQ-6) score performed at weeks 0, 8, 24, and 36 or early withdrawal visit

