### **6.3.2. Spirometry**

#### **6.3.2.1. Definition**

Pre-bronchodilator (on designated clinic visit days per Table 1 of the protocol; Screening/Baseline and week 8, 24, and 36 or early withdrawal visit) and daily morning ambulatory FEV1 will be measured using the handheld device that has combined spirometry and eDiary capabilities. The FEV1 is the volume of air that can be forcibly exhaled from the lungs in the first second, measured in liters. The National Health and Nutrition Survey (NHANES) III reference equations will be used.

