### **6.3.5.2. Analysis**

Summary statistics of actual values and changes from baseline to each scheduled visit in ACQ-6 score will be provided by previous double-blind treatment group and for all patients. A line graph presenting the mean change from baseline over time (at each visit) will be provided for the overall score by previous double-blind treatment group.

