### **6.3.6.1.1. Missing data handling and total score calculation**

The overall and domain scores of the AQLQ +12 are derived as the average of the corresponding items; the analysis will be based on the available data.

For incomplete data, the overall AQLQ +12 score for a particular visit will not be calculated if 3 or more responses are missing with no more than 1 per domain. For the symptom and activity domain total scores, calculation will require no more than 1 missing item. Total scores for the other 2 domains will be regarded as missing if 1 or more item is missing.

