### **6.3.6.2. Analysis**

Summary statistics of actual values and change from baseline to each scheduled visit in the overall and domain scores of AQLQ + 12 will be provided by previous double-blind treatment group and for all patients. A line graph presenting the mean change from baseline over time (at each visit) will be provided for the overall score by previous double-blind treatment group.

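### SAP 4.4 places early-termination clinic FEV1, ACQ-6 and AQLQ12+ values by time since last dose alone, so four of nine last-dose positions appear under week 8 or 24 although seen 3 to 13 weeks earlier; separately, the AQLQ12+ overall-score rule, read literally, scores any partly completed form with 5 or more blanks

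*SAP*

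**What the plan says.** **Visit labels.** For efficacy by-visit summaries, SAP 4.4 uses scheduled visits, with one exception. An early-termination value "will be considered as the next scheduled visit for that assessment if at least 3, but no more than 5 weeks, elapsed since" the last dose. The same section defines an *Endpoint* summary as the last observation in the treatment period. For patients who stop early, "the treatment period will be defined from the first dose of study drug to the last dose of study drug + 4 weeks".

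**Schedule of the three measures.** SAP 1.1 lists clinic FEV1 as "measured using spirometry at weeks 0, 8, 24, and 36 or early withdrawal visit", and SAP 6.3.2.1 repeats it as "Screening/Baseline and week 8, 24, and 36 or early withdrawal visit". ACQ-6 and AQLQ12+ follow the same weeks. The Protocol Appendix B list for Visits 2 to 9 confirms this for the questionnaires: "Complete asthma-specific tests (ACQ-6 and AQLQ12+) (week 8 and 24 only". Dosing is every 4 weeks for 9 doses (Protocol 5.1.1).

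**Outputs.** For ACQ-6, "Summary statistics of actual values and changes from baseline to each scheduled visit in ACQ-6 score will be provided" (SAP 6.3.5.2). For AQLQ12+, "A line graph presenting the mean change from baseline over time (at each visit) will be provided for the overall score" (SAP 6.3.6.2). SAP 6.3.2.2 treats clinic FEV1 likewise. None of these three analysis sections mentions *Endpoint*.

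**AQLQ12+ overall score.** SAP 6.3.6.1.1 says the overall score "will not be calculated if 3 or more responses are missing with no more than 1 per domain". Symptom and activity domain scores tolerate one missing item; the other two domains tolerate none.

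**The concern.** A 3-5-week limit suits something measured at every 4-weekly visit, because the early-termination visit then falls close to the visit it replaces. These three measures are 8 to 16 weeks apart. A value can meet the time-since-dose condition and still be far from the week it is shown under. By-visit means and mean-change graphs for three secondary efficacy measures can therefore include earlier values, from withdrawn patients only, under a later week. SAP 2.5.1 also plans these outputs for the interim report supporting the sBLA.

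The AQLQ12+ sentence is a separate matter. As written, it blocks some forms with three well-spread blanks and passes forms that are mostly empty. Two programmers could score the same form differently.

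**Working it through.** **Inputs.** Doses at weeks 0, 4, ..., 32 (Protocol 5.1.1 and Table 1). Early-termination window of 3 to 5 weeks after last dose (SAP 4.4). Post-baseline schedule {8, 24, 36} (SAP 1.1, 6.3.2.1). Visit windows ±7 days (Protocol Table 1). AQLQ12+ items per domain: symptoms 12, activity 11, emotional 5, environmental 4 (SAP 6.3.6.1).

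**Reproducing the plan's figures.** Doses: 32/4 + 1 = 9, as stated. End of study: 32 + 19 = week 51, as stated. Items: 12 + 11 + 5 + 4 = 32, as stated.

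**Part 1.** For last dose at week L, the visit falls at L+3 to L+5. The label is the first of 8, 24, 36 after L. Gap = label week minus visit week.

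| Last dose | Seen (weeks) | Label | Gap, nominal dates | Gap, doses after week 0 given ±7 days |
|---|---|---|---|---|
| 0 | 3-5 | 8 | 3 to 5 | 3 to 5 |
| 4 | 7-9 | 8 | -1 to 1 | -2 to 2 |
| 8 | 11-13 | 24 | 11 to 13 | 10 to 14 |
| 12 | 15-17 | 24 | 7 to 9 | 6 to 10 |
| 16 | 19-21 | 24 | 3 to 5 | 2 to 6 |
| 20 | 23-25 | 24 | -1 to 1 | -2 to 2 |
| 24 | 27-29 | 36 | 7 to 9 | 6 to 10 |
| 28 | 31-33 | 36 | 3 to 5 | 2 to 6 |
| 32 | 35-37 | 36 | -1 to 1 | -2 to 2 |

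Three positions (weeks 4, 20, 32) are labelled within a week on nominal dates. Two (weeks 24, 28) are shown under week 36 early, but the endpoint is defined as week 36 or early withdrawal. Four (weeks 0, 8, 12, 16) are shown under week 8 or 24 with no such cover. Their gaps are 3 to 13 weeks nominally, and 2 to 14 weeks with the dosing window.

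*Next* is counted from the last dose here. Counted from the termination visit, a patient last dosed at week 4 and seen just after week 8 would be labelled week 24, almost 16 weeks on. The reading used is the milder one.

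**Checking the window condition.** Week 8 spans weeks 7-9 and week 24 spans weeks 23-25. On nominal dates, values after last doses at weeks 4 and 20 all stay. The latest possible visits for the four positions, with dosing a week late where allowed, are weeks 5, 14, 18 and 22. The first is 2 weeks short of week 7; the others are at least 1 week short of week 23. None enters.

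**Part 2.** Literal rule: withhold if blanks ≥ 3 and no domain has more than 1 blank.

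- 3 blanks: withheld patterns = 12×11×5 + 12×11×4 + 12×5×4 + 11×5×4 = 1648 of 4960. Scored = 3312.
- 4 blanks: withheld = 12×11×5×4 = 2640 of 35960. Scored = 33320.
- 5 or more blanks: with 4 domains, at least one domain has 2 blanks, so nothing is withheld.
- All four domain scores are missing when blanks are at least 2 + 2 + 1 + 1 = 6. At 6 blanks this is 66×55×5×4 = 72600 of 906192 patterns, each still given an overall score.

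**The case against.** **The labelling rule is explicit and pre-specified.** It ties the label to each assessment's own schedule, and the SAP does not contradict itself. That is right, but a clearly stated rule can still put a week 11-13 value in the week 24 row.

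**Six of nine would overstate it.** A reader of the table might count every gap of 3 weeks or more and infer that six positions are mislabelled. The documents do not support this: the endpoint wording covers weeks 24 and 28. Nor is the distance unbounded, since the schedule itself caps the nominal gap at 13 weeks.

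**An *Endpoint* summary already exists.** SAP 4.4 defines it for efficacy summaries, but the three analysis sections name only scheduled visits, so it is not clear that it will be tabulated for these measures.

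**A window treats withdrawals more strictly than scheduled visits.** The SAP sets no analysis window for a scheduled visit made late, and dropping withdrawn patients moves the by-visit rows towards patients still attending. Both points stand as costs. A late scheduled visit does have a nominal week, though, whereas a termination visit has none until a rule gives it one. The *Endpoint* row recovers most displaced values.

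**The AQLQ12+ point is a separate drafting slip.** Agreed; it adds no weight to the first part. The questionnaire is not shown and the intended threshold cannot be settled from these documents, so the sponsor must confirm it.

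**Conclusion.** Both parts hold within a limited scope.

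1. For clinic FEV1, ACQ-6 and AQLQ12+, four of nine last-dose positions receive a week 8 or week 24 label that nothing else in the documents supports: one at 11-13 weeks, one at 7-9 and two at 3-5, on nominal dates.
2. The AQLQ12+ overall-score rule, read literally, never withholds a partly completed form with 5 or more blanks.

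The result rests on counting the next visit from the last dose, and on the literal wording of SAP 6.3.6.1.1. The counts are of dosing positions and blank patterns, not patients or forms. A reader might infer that the by-visit means are biased in a known direction, or that many questionnaires would be mis-scored. The documents give no dropout or item-missing rate, so neither follows. All analyses are descriptive, no test or decision rule uses these tables, and the primary adverse-event endpoint is unaffected. The wording should be corrected because it yields wrong table entries and is cheap to change.

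**What to change.** **SAP 4.4.** Keep the 3-5-week condition and state that *next* is counted from the last dose. Add that an early-termination clinic FEV1, ACQ-6 or AQLQ12+ value is assigned to week 8 or week 24 only if it also falls within that visit's ±7-day window in Protocol Table 1; otherwise it is not shown under week 8 or 24. Where the next scheduled visit is week 36, leave the present rule unchanged and title the row *Week 36 or early withdrawal*. Do not pool all early withdrawals in that row: a patient last dosed at week 0 and seen at week 3 would be 36 - 3 = 33 weeks from the label.

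**SAP 6.3.2.2, 6.3.5.2 and 6.3.6.2.** Add the *Endpoint* row that SAP 4.4 already defines, so that displaced values still contribute if taken within the treatment period.

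**SAP 6.3.6.1.1.** After the sponsor confirms the threshold, replace the sentence with: *The overall score will be calculated only if fewer than 3 responses are missing and no domain has more than 1 missing.*

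**Cost.** SAP wording and one extra row in three sets of tables; no new data.

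- The n at weeks 8 and 24 is slightly smaller.
- Displaced values taken more than 4 and up to 5 weeks after the last dose are listed only.
- If the week 4 or 20 dose was off schedule, the visit can fall at weeks 6-10 or 22-26, and values outside weeks 7-9 or 23-25 lose their label.
- The AQLQ12+ wording withholds 66 + 55 + 10 + 6 = 137 of 496 two-blank patterns that the literal text scores. This tightens the rule as well as clarifying it, which is why confirmation comes first.
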